2.1.1 Reporting Precision

Summary statistics will be presented to the degree of precision specified in Table 1, unless otherwise specified:

Table 1: Reporting Precision

Statistics	Degree of Precision
Mean, Median, Quartiles, Confidence limit boundaries	One decimal place more than the raw data.
Standard deviation	Two decimal places more than the raw data.
Minimum, Maximum	The same as the raw data.
p-value	Rounded to 4 decimal places and therefore presented as 0.xxxx; p-values smaller than 0.0001 as '<0.0001'; p-values greater than 0.9999 as '>0.9999'.
Percentage	One decimal place. A percentage of 100% will be reported as 100%. Percentages of zero will be reported as 0.

For weight and height, one decimal place will be used for summary statistics. Fractional numeric values will be presented with a zero to the left of the decimal point (for example, 0.12 – 0.30).

2.2 DEFINITIONS OF ANALYSIS POPULATIONS (ANALYSIS SETS)

2.2.1 Randomized Population

The randomized population comprises all subjects who are randomized to one of GNX or PBO treatment group.

2.2.2 Intention-to-Treat Population (ITT)

The ITT population comprises all randomized subjects who received at least one dose of study drug and have at least one post-baseline efficacy assessment.

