2.2.3 Safety Population

The Safety population comprises all randomized subjects who received at least one dose of study drug.

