2.2.4 Per-Protocol Population (PP)

The PP population includes all ITT subjects without major protocol violations (defined prior to database lock). There will be no PP population for the OL phase of the study.

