7.1 DOUBLE-BLIND PHASE

All efficacy analyses will be conducted in the ITT population as well as by biomarker stratum. A supportive analysis of the primary efficacy endpoint also will be conducted in

the PP population.

All analyses in the ITT population will include all available data, even if they were collected after the subject stopped taking study medication, regardless of whether the subject took rescue medication. Section 7.1.1 details the handling of missing data.

For the analyses of seizures, the baseline phase consists of the 8- to 12-week period before the first day of treatment, and the DB phase starts the day following the first day of DB treatment until the final visit for subjects who do not enter the OL and up to the day before the first dose of OL treatment for those who do. Also, if a subject's baseline primary seizure count based on the prospective baseline period is less than 4, the primary seizure count from the Historical Seizure Calendar Review CRF will be used to calculate a baseline 28-day seizure count.

Tests of significance between the two treatment groups will be performed for the primary endpoint with a 2-sided significance level of 0.05.

Seizure diary compliance for the baseline and post-baseline DB phase intervals will be calculated as:

$100 \times (\text{Number of Days with Available Seizure Diary}) / (\text{Last Available Seizure Diary Date} - \text{First Available Seizure Diary Date} + 1)$.

Seizure diary compliance between visits will be calculated as:

$100 \times (\text{Number of days with available seizure data between visits}) / \text{Number of days between visits}$, with the days between visits defined as the day of the prior visit up to the day before the current visit.

Diary compliance values will be summarized with descriptive statistics and the percentage of subjects at least 80% compliant.

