7.1.6 Sensitivity Analyses

Two sensitivity analyses of the primary efficacy endpoint of change in 28-day frequency of the primary (i.e., all countable motor) seizure types will be performed:

Intermittent (random/sporadic) missing data during the 17-week DB phase and any missing data during the baseline phase will be assumed missing completely at random and the collected data will be used to calculate the 28-day seizure frequencies. For early drug termination prior to the end of the 17-week DB phase, caregivers will be instructed to continue to provide daily seizure records until the end of the 17-week DB phase (hence further preventing missingness).

In the first sensitivity analysis, the following imputation approach will be used for the primary outcome measure when a subject stops recording measurements permanently (anticipated to be zero or minimal in occurrence) prior to the end of the 17-week DB phase. For days with missing seizure count data, the corresponding median PBO data will be imputed (irrespective of treatment arm), within each stratum, as follows:

- Compute the median 28-day seizure frequency in the PBO arm based on all available PBO measurements during the 17-week DB treatment phase. Label that

‘X’ and define ‘A’ to be ‘X’/28, (i.e., the daily average on placebo during the 17-week during the DB phase).

- For any days (whether they be in the PBO or GNX arm) that occur AFTER a subject has become lost to follow up, impute ‘A’ on that day.

The second sensitivity analysis will explore the possibility that subjects who stop recording their seizure counts tend to have higher seizure counts than the other subjects. The imputation method described above will be modified to use the median of the 5 highest counts, rather than the median count, among the PBO subjects with data.

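### A randomized child who was never dosed, or has no post-baseline efficacy assessment, is in neither the primary result nor its missing-data sensitivity analyses

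*SAP*

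**What the plan says.** SAP 2.2 defines four analysis sets.

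- **Randomized (2.2.1):** "The randomized population comprises all subjects who are randomized to one of GNX or PBO treatment group".
- **ITT (2.2.2):** "all randomized subjects who received at least one dose of study drug and have at least one post-baseline efficacy assessment". Protocol 9.6 has the same definition.
- **Safety (2.2.3):** "The Safety population comprises all randomized subjects who received at least one dose of study drug".
- **Per-protocol (2.2.4):** "The PP population includes all ITT subjects without major protocol violations (defined prior to database lock"), so it is a subset of ITT.

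SAP 7.1 then states: "All efficacy analyses will be conducted in the ITT population as well as by biomarker stratum". The supportive analysis of the primary endpoint uses the per-protocol set.

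SAP 7.1.6 plans "Two sensitivity analyses of the primary efficacy endpoint of change in 28-day frequency of the primary" seizure types and names no population. The imputation applies "when a subject stops recording measurements permanently" before the end of the double-blind phase. It fills the days "that occur AFTER a subject has become lost to follow up", in either arm, with a daily value derived from the placebo median 28-day frequency in the child's stratum. The second analysis replaces that median with the median of the five highest placebo counts.

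The disposition summary in SAP 3.1 is by double-blind treatment group. It has rows for Safety, ITT and PP, and for study and drug discontinuation with reasons. It has no row for randomized children. All randomized children appear in two listings: dispositions (3.1) and source data with derived efficacy variables (2.1).

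**The concern.** Membership of ITT depends on two events after randomization: taking a dose and providing a post-baseline efficacy assessment. That is a common choice for a primary analysis. The difficulty is that the same filter carries over to the sensitivity analyses. Those analyses exist for children whose recording stops, and the extreme case, a child with no post-baseline record at all, is removed before any imputation starts.

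In a trial of about 25 children, one exclusion matters to a rank test. The two arms need not lose such children equally. A sensitivity analysis that cannot contain them cannot show whether the primary result depends on leaving them out. The Randomized population that would close the gap is already defined, but no table uses it.

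**Working it through.** **1. Who falls outside.** SAP 2.1 starts post-baseline seizure data on the day after the first double-blind dosing day (Day 0). Reading 2.2 with 7.1 and 7.1.6:

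| Randomized child | Safety | ITT | Primary analysis | 7.1.6 analyses |
|---|---|---|---|---|
| Never dosed | no | no | out | out |
| Dosed, no diary day after Day 0 (and no other post-baseline efficacy assessment) | yes | no | out | out |
| Dosed, one diary day after Day 0, then lost | yes | yes (natural reading) | in | in, later days imputed |

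Only the first two rows are affected. The last two columns rest on 7.1 governing 7.1.6, because 7.1.6 itself is silent on population.

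**2. What the tables show.** For dosed children, Safety N minus ITT N in each arm (both rows are in SAP 3.1) gives the number excluded. Never-dosed children have no row, and no row gives the reason for exclusion from ITT.

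**3. Weight of one child.** SAP 1.3.1 expects about 25 randomized 1:1, so 12 or 13 per arm. One child is 1/25 = 4% of the trial, and 1/12 = 8.3% or 1/13 = 7.7% of an arm.

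**4. Illustrative effect on the test.** The documents give no figure to reproduce here. Assume 12 GNX and 13 placebo randomized, with one GNX child outside ITT. Let U be the number of GNX–placebo pairs in which the GNX child has the worse percent change. Take the exact two-sided Wilcoxon distribution with no ties, and alpha 0.05 two-sided (SAP 7.1).

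- Child omitted: 11 v 13, U = 33, p = 0.0257.
- Added at the placebo median percent change: she is worse than 6 of the 13 placebo children, so U = 33 + 6 = 39. At 12 v 13, p = 0.0345. Placed just above the median child instead, U = 40 and p = 0.0398.
- Added at the worst rank: she is worse than all 13, so U = 33 + 13 = 46. At 12 v 13, p = 0.0868.

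Significance survives the first placement and is lost under the second.

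**5. Why the 7.1.6 rule should not simply be extended to every day.** The rule imputes a placebo *frequency* X, while the endpoint is a *percent change*. For a child imputed on all double-blind days, with baseline frequency B:

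percent change = 100 × (X − B) / B

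With X = 5 per 28 days (assumed):

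- B = 20 gives 100 × (5 − 20)/20 = −75%. A child with no data is scored as a 75% reduction.
- B = 4 gives 100 × (5 − 4)/4 = +25%.

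A simulation assumed lognormal baselines with log-SD 0.8 to 1.2, and placebo percent changes with mean 0 and SD 40. A wholly imputed child received a reduction of 50% or more in about 24% to 32% of trials. The documents do not give the baseline spread, so this range depends on those assumptions.

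**The case against.** The strongest reply is that the gap barely exists. Several stronger readings are tempting, and the documents do not support them.

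- **That a child who leaves in the first days, for example because of sedation, is lost to the sensitivity analyses.** Normally she is not. The diary is daily (Protocol 7.4.1), there is a Day 3 call with diary review (Protocol 7.2.2.1), and late and proxy entry are possible (Protocol 9.1). Caregivers are told to keep recording after the drug is stopped (SAP 7.1.6). One diary day after Day 0 appears to put her in ITT, and her later days are then imputed.
- **That an imbalance in exclusions between arms would appear in no table.** For dosed children it would, by subtracting ITT from Safety within arm, and the discontinuation reasons are in the same table. Only never-dosed children and the specific reason for ITT exclusion are missing.
- **That SAP 7.1.6 restricts itself to ITT.** It does not say so. The restriction is inferred from 7.1, though no other population is offered.
- **That a lost child would overturn the result.** Worst rank is not a rule in either document, and at the placebo median percent change the example stays significant.

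The SAP also expects permanent cessation of recording to be zero or minimal.

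All of this stands, and it limits how often the gap could matter. It does not remove the gap: a child with no post-baseline efficacy assessment, or no dose, is outside every planned efficacy analysis.

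**Conclusion.** The point holds as a minor, inexpensive improvement. It does not invalidate the primary analysis. ITT as defined excludes never-dosed children and children with no post-baseline efficacy assessment, and on the natural reading of SAP 7.1 the sensitivity analyses inherit that exclusion.

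The number affected is unknown and may be zero, in which case no result changes. If there is one such GNX child and the result is near the threshold, the illustration moves p from 0.026 to between 0.035 (placebo median percent change) and 0.087 (worst rank). These figures assume 11 v 13 analysed, no ties, and a single excluded child in the GNX arm. They are not forecasts.

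The conclusion also assumes that a diary day counts as an efficacy assessment, which the SAP does not state. If it does not count, more children could be affected.

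**What to change.** Keep ITT as the primary population, and make these changes to the SAP.

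1. **Section 7.1.6, population.** State that both sensitivity analyses of the primary endpoint use the Randomized population of 2.2.1.
2. **Section 7.1.6, imputation for a child with no post-baseline diary.** Impute on the percent-change scale so that she cannot be credited with a response. For example, use the placebo median percent change in the first analysis, and an unfavourable placebo value or the worst rank in the second. Do not apply the placebo median frequency to all her days, for the reason in step 5 of the working. The present day-by-day rule can stay for children with some post-baseline diary data.
3. **Section 3.1, disposition.** Add two rows by arm: *Subjects randomized*, and *Randomized but not in ITT, with reason*.

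The cost is a few lines of text, one changed population flag and two table rows. The downside is that such a child enters wholly on imputed values, which is acceptable in a sensitivity analysis. If there is no such child, the results are unchanged and the disposition table shows it.

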2.2.3 Safety Population

The Safety population comprises all randomized subjects who received at least one dose of study drug.

2.2.4 Per-Protocol Population (PP)

The PP population includes all ITT subjects without major protocol violations (defined prior to database lock). There will be no PP population for the OL phase of the study.

2.3 TIME WINDOWS FOR ANALYSIS

For by-visit safety or efficacy summaries, only scheduled visits will be analyzed.

In the analysis of seizure diary data, entries after the date of the first dose of study drug in the DB phase of the study but prior to the date of the first dose of study drug in the OL phase will be considered DB data. For subjects participating in the OL phase, entries dated after the date of first dose of study drug in the OL phase, including during the OL titration period, will be considered OL data.

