7.6.5. Clinical Laboratory Tests

Clinical laboratory tests are listed in Section 12.2 and will be collected per the schedules listed in Table 1 and Table 2. If any test result is unexpectedly out of range, a repeat test can be performed at any time as decided by the PI to confirm the initial result.

The following liver function and eGFR tests will be monitored throughout the study as follows.

- If AST or ALT increases > 3 times ULN during the study, subject should be followed with weekly laboratory repeat testing and continue in study if levels trending down. Subject will be discontinued if levels do not decline to under $3 \times$ ULN.
- If total bilirubin increases to $1.5 \times$ ULN or more during study, the subject will be discontinued.
- Subjects with significant renal insufficiency, eGFR < 30 mL/min (calculated using the Cockcroft-Gault formula), will be discontinued if the criterion is met post baseline.

If any of the criteria above are deemed clinically significant by the PI, then the sponsor's medical monitor should be contacted.

Due to the difficulty in obtaining urine samples, urinalysis will be conducted as follows: during the DB phase at Visit 1 (screening) or baseline/randomization (Visit 2), Visit 3, and at Week 17 (Visit 5; also Final DB Visit/First OL Visit in OL phase); in the OL phase at Visit 7 (Week 36), Visit 8 (Week 52) and annually thereafter, or at the Safety Follow-up Post-Taper visit if IP is discontinued; and at the Final OL Visit. An attempt will be made to collect a urine sample at screening to perform the study-related urinalysis. Otherwise, the urine sample for the urinalysis can be collected at baseline.

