7.1.1 Handling of Missing Data

The primary analysis will use all available data. Careful educating and monitoring of the study sites will attempt to limit the amount of missing data. Sensitivity analyses, with replacement of missing data, will be performed for the primary efficacy endpoint; see Section 7.1.6.

For non-seizure variables, data for subjects prematurely discontinuing from the study will be assigned to the first visit subsequent to the discontinuation at which the assessment was scheduled, as long as the discontinuation visit is within 32 days of the next scheduled performance of that assessment.

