9 SAFETY ANALYSIS

All safety analyses will be performed in the Safety Population. The results in the DB and OL phases will be summarized separately. In both phases, the results will be summarized by the DB treatment actually received and, for the OL phase of the study, combined over the treatment groups. Baseline for safety endpoints is defined as the last non-missing value obtained before the first day of DB treatment. Assessments performed at multiple post-baseline time points will be summarized at each time point for which they are scheduled, but the listings will also include any assessments performed at unscheduled time points.

The number and percentage of days that subjects received investigational product, the highest percentage of the maximum allowable daily dose (1800 mg or 63 mg/kg) that subjects received, and the total amount of investigational product received will be summarized. For the OL phase, they will be summarized over just the OL phase as well as over the entire study (combined DB and OL phases) but the classification by the DB treatment applies only for the OL phase summary. The summarization over the entire study will include only subjects who were in the GNX group during the DB phase, regardless of whether they entered the OL, and all the subjects from the OL phase. A subject data listing will be provided with full details of the study drug dispensation.

Safety assessments include:

- AEs
- Clinical laboratory tests
- Vital signs including BP, HR, RR, body temperature, weight, and height
- 12-lead Electrocardiogram (ECG)
- Physical, neurological and developmental examinations
- Neurosteroid levels
- Tanner staging (OL phase only)

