9.2 CLINICAL LABORATORY PARAMETERS

Laboratory assessments include hematology, clinical chemistry, and urinalysis:

- Clinical Chemistry: Total Bilirubin, Aspartate Aminotransferase (AST), Alanine Aminotransferase (ALT), Blood Urea Nitrogen (BUN), Glucose, Potassium, Sodium, Calcium, Alkaline Phosphatase, Chloride, Creatinine, Carbon Dioxide (CO2).
- Hematology: Hemoglobin, Hematocrit, Erythrocytes, Leukocytes + differential, Thrombocytes (platelet count).
- Urinalysis: pH, Color, Transparency, Specific Gravity, Urobilinogen, Ketones, Protein, Glucose

All laboratory parameters will be presented in Système International (SI) units.

Quantitative results (including actual values and change from baseline) will be summarized using descriptive statistics by baseline and post-baseline visit for each laboratory test group above. Laboratory test results will be assigned an LH classification according to whether the value was below (L) or above (H) the normal reference range (some urinalysis labs are assigned only normal and abnormal classifications) (See also Appendix 14.2). Values outside the normal range will also be classified as to whether

they were potentially clinically significant (Appendix 14.3). Shift tables cross-tabulating the baseline and post-baseline classifications (below (L), Normal (N), or above (H) the reference range), by visit, will be provided.

All laboratory data will be included in the listings. A pregnancy listing will be provided separately.

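### Laboratory, vital-sign and ECG tables use scheduled visits only, and no table counts subjects who ever crossed an Appendix 14.3 threshold

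*SAP*

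**What the plan says.** - **Which visits are tabulated.** SAP 2.3: "For by-visit safety or efficacy summaries, only scheduled visits will be analyzed". SAP 9 says of all safety assessments: "Assessments performed at multiple post-baseline time points will be summarized at each time point for which they are scheduled", and continues "but the listings will also include any assessments performed at unscheduled time points".
- **Laboratory tables.** Under SAP 9.2, values and changes are "summarized using descriptive statistics by baseline and post-baseline visit for each laboratory test group above". The only other laboratory table is the shift table: "Shift tables cross-tabulating the baseline and post-baseline classifications (below (L), Normal (N), or above (H) the reference range), by visit, will be provided".
- **Vital signs and ECG.** SAP 9.3.1 and 9.3.2 summarise values and changes by visit. The ECG interpretation categories are also by visit.
- **Clinical-significance criteria.** SAP 9.2 classifies out-of-range laboratory values against Appendix 14.3 but names no table for the result. Appendix 14.3.2 and 14.3.3 give ECG and vital-sign criteria, and 14.3.2 mentions a QT prolongation analysis. SAP 9.3.1 and 9.3.2 refer to neither.
- **Off-schedule tests.** Protocol 7.6.5 says that after AST or ALT above 3 x ULN the "subject should be followed with weekly laboratory repeat testing and continue in study if levels trending down", with discontinuation if levels do not fall below that limit. It also allows any unexpected out-of-range result to be repeated at any time.
- **Early termination.** SAP 7.1.1, in the efficacy section, assigns non-seizure data from subjects leaving the study to the next visit at which the assessment was due, "as long as the discontinuation visit is within 32 days of the next scheduled performance of that assessment". It gives no destination for data outside that window.

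**The concern.** The protocol creates off-schedule results that bear on whether a child stays on treatment, and the SAP keeps those results out of every laboratory, vital-sign and ECG table. Take a child who is in range at Week 9, is found raised at an unscheduled test, and is back in range at Week 17. The shift table shows her as normal throughout.

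A second gap exists even when the abnormal value falls at a scheduled visit. A low/normal/high table puts an AST just above ULN and an AST at 5 x ULN in the same cell. The by-visit maximum (SAP 2.1) shows one value, not how many subjects crossed the limit.

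Safety and tolerability are secondary objectives in both phases. The sponsor's own background text (Protocol 1.2) reports the percentage of subjects by arm with AST or ALT above 3 x ULN during earlier studies. This SAP defines no table that would give the same figure for this trial.

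**Working it through.** The documents give no figure to reproduce, so the check traces the rules and then counts days.

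**1. Is there an any-time table?** SAP 2.3 on its own limits only by-visit summaries and would permit an any-time table. Reading on through SAP 9, 9.2, 9.3.1, 9.3.2 and 14.3, no worst-value, maximum-per-subject or ever-met-criterion table is defined for laboratory tests, vital signs or ECG.

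**2. How much off-schedule testing can occur?** Post-baseline double-blind chemistry and haematology are at Weeks 5, 9 and 17 (Protocol Table 1). Weekly repeats strictly between two visits number (later week - earlier week - 1): 4 before Week 5, 3 between Weeks 5 and 9, and 7 between Weeks 9 and 17. Open-label gaps of 15 and 16 weeks allow 14 and 15.

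**3. Which early-termination tests are unmapped, if the 32-day rule covers safety data?** Nominal day = 7 x week. A day strictly between visits is unmapped when (next scheduled day - day) > 32.

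| Double-blind interval | Days between | Unmapped days |
|---|---|---|
| Laboratory, Weeks 0-5 | 34 | 2 (days 1-2) |
| Laboratory, Weeks 5-9 | 27 | 0 |
| Laboratory, Weeks 9-17 | 55 | 23 (days 64-86) |
| **Laboratory total** | **116** | **25 (25/116 = 22%)** |
| ECG, Weeks 0-5 | 34 | 2 (days 1-2) |
| ECG, Weeks 5-17 | 83 | 51 (days 36-86) |
| **ECG total** | **117** | **53 (53/117 = 45%)** |

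Vital signs share the laboratory visits. The same count for the open-label phase gives 230 of 353 days (65%) for laboratory tests to Week 68 and 184 of 243 (76%) for ECG to Week 52. Those two figures apply only if an early discontinuation is not tabulated in the Final OL/early D/C column of Protocol Table 2.

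**4. How often would a transient abnormality meet a scheduled test?** Assume onset is uniform over days 1-119. An abnormality lasting L days overlaps a scheduled test with probability (number of tests x L)/119, because the windows before each test do not overlap for the values used here.

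- L = 14: laboratory 3 x 14/119 = 35%; ECG 2 x 14/119 = 24%.
- L = 28: laboratory 3 x 28/119 = 71%; ECG 2 x 28/119 = 47%.

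These are illustrations of visit spacing, not forecasts for this trial.

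**5. What is one subject worth?** About 25 randomised 1:1 is about 12 per arm, and 1/12 is about 8 percentage points. If the 0.3% rate of raised AST or ALT on ganaxolone in Protocol 1.2 applied here (an assumption, since those populations differ), 12 x 0.003 is about 0.04 expected cases.

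Protocol 4.5.1 and 7.6.5 describe different consequences of a bilirubin rise to 1.5 x ULN (weekly repeats in one, discontinuation in the other). These passages must be reconciled, because they determine which unscheduled bilirubin tests will exist.

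**The case against.** The case on the other side is substantial, and most of it stands as a limit on size.

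- **Nothing is lost.** The listings carry every laboratory value and every unscheduled assessment, and about 25 subjects can be read by hand. This stands.
- **Adverse-event tables.** A reader might infer that off-schedule results reach no table at all. The documents do not support that. Protocol 8.1.5 lets a clinically significant or normal-to-abnormal change be recorded as an adverse event. SAP 9.1 tabulates adverse events, including those leading to drug discontinuation or dose reduction. That route depends on investigator judgement, so it does not replace a count against a fixed threshold.
- **The liver rule.** A reader might infer that the weekly repeats remove liver cases from the shift tables. If the triggering value came from a scheduled visit, the child is already classed as high and a later peak cannot change her cell. Subjects are missed only when the abnormality first appears off schedule.
- **Direction of error.** A reader might infer that the rule always lowers abnormality counts. It does not, because a scheduled value that a repeat fails to confirm still counts as abnormal. The rule is the same in both arms, and no between-arm bias is shown.
- **Withdrawn children.** A reader might infer that a child taken off drug on an unscheduled result is tabulated as missing. Subjects who stop drug in the double-blind phase remain in follow-up and are encouraged to attend scheduled visits (Protocol 3.1, 4.5; Table 1 note q). The 32-day rule concerns those leaving the study.
- **Larger shares.** Using the Week 9 to 17 gap alone would give (56 - 32)/56 = 43%, but the figure over all double-blind between-visit days is 22%.

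The missing threshold count is not answered by any of these points.

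**Conclusion.** The point holds as a reporting gap. An abnormality first seen at an unscheduled or unmapped early-termination test is absent from the laboratory, vital-sign and ECG tables. No table counts subjects who ever met an Appendix 14.3 criterion.

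The 22% (laboratory) and 45% (ECG) shares are shares of days, not of subjects. They rest on nominal visit days and on the 32-day rule applying to safety data, which its position in the efficacy section leaves open. If it does not apply, the SAP has no stated rule for placing early-termination safety tests.

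The number of subjects affected may well be zero. The gap concerns what the safety report can show, and it does not call the safety conclusions into doubt. It is worth closing because closing it costs little.

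**What to change.** Keep the by-visit tables as they are; the SAP 2.3 sentence already confines itself to them and needs no change. In SAP 9.2, 9.3.1 and 9.3.2 add the following, by phase and treatment, using all scheduled, unscheduled, early-termination and local-laboratory values:

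- for laboratory tests, vital signs and ECG measurements, shift from baseline to the worst low and to the worst high post-baseline value;
- n (%) of subjects meeting each Appendix 14.3 criterion at any time post-baseline, including AST, ALT, bilirubin and QTc.

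State in SAP 7.1.1 or 9 whether the 32-day rule applies to safety data, and where early-termination results outside the window are shown.

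The cost is SAP wording and a few tables from data already collected. Abnormality rates may look slightly less favourable, and the any-time counts will include values not confirmed on repeat.
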